5.1 Inclusion criteria

Extreme premature infants <32 weeks and <1500g, cared at BCNatal Hospital Clinic during years 2014-2019. Participants will have to survive beyond 7 days of life (moment where the probiotic intervention will be given). Recruitment will start from January 2014 and will last until December 2019.

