3.1 Main and secondary variables

- Gestational age, weight, length and head circumference at birth
- Sex
- Multiple gestation

- Gestational pathology (diabetes, preeclampsia, maternal sepsis, placental disease, in vitro fecundation)
- IUGR and degree of IUGR
- Inborn vs Outborn
- Apgar at 5 and 10 minutes
- Antenatal steroids
- Type of delivery (vaginal vs caesarean)
- Coriamnionitis
- Type of feed (breastfeeding, donor milk or formula)
- Duration of breastfeeding
- Necrotising enterocolitis, early and late-onset sepsis, mortality
- Antibiotic use beyond 48 hours of life
- Days of parenteral nutrition
- Days of enteral nutrition
- Days of invasive ventilation, days of non-invasive ventilation, days of oxygen
- Days of stay in intensive care
- Chronic lung disease
- Intraventricular haemorrhage (I-IV)
- Periventricular leukomalacia
- Cranial ultrasound result
- Retinopathy of prematurity
- Neurosensorial hearing loss
- Cerebral palsy
- Colic in early infancy
- Bayley score at 2 years of age
- MRI at 2-3 years of age
- Growth chart
- Moment of “catch-up”
- Childhood diseases (asthma, atopic skin, hospital admissions, allergy,...)
- Need for antibiotics or probiotics during childhood >48 hours
- Weight and height at the assessment
- WISC-V at 6 years
- CBCL 6-18 (Child Behaviour Checklist 6-18)
- BRIEF-2
- Mother tongue
- Parental age
- Cultural level of parents
- Ethnical origin
- Parents work
- Kind of family (single parent, ...)
- Social services requirements
- Need to attend early stimulation centre

4 Study design

Quasi-experimental, sequential, unicentric, cohort study with the performance of neuropsychological tests and biomarkers of neurodevelopment, inflammation, and intestinal permeability.

We estimate an initial phase of 2 years with a comparison at 6 years of age (4 years after start of trial).

5 Enrolment of participants

Infants born below 32 weeks gestational age and birth weight under 1500g cared for at BCNatal Hospital Clínic (tertiary neonatal unit) in Barcelona between January 2014 and December 2019. There will be a 12 month wash out period (year 2017) to alleviate cross contamination of probiotics.

Participants will be contacted via phone (parent/legal guardian) for those that consented to be included for a 6-year assessment and blood sampling. In those cases where contact via phone has not been possible, contact to reference Paediatrician will be sought.

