5.2 Exclusion criteria

All neonates presenting with suspected congenital anomalies, inborn errors of metabolism, or genetic defects will be excluded. Infants with a suspected syndrome, or who had suffered events beyond the neonatal period, not related to prematurity, that could entail impairment in neurodevelopment (severe cranioencephalic trauma, oncological process, meningitis, or exposure to toxic substances) will also be excluded.

6 Treatment and study calendar

Intervention

Daily dose of 6x10⁹ UFC Infloran® -Berne, Switzerland- (Bifidobacterium bifidum NCDO 2203 and Lactobacillus acidophilus NCDO 1748) from 7 days of life until reaching a postmenstrual age of 34 weeks or discharge. The probiotic mixture will be provided in capsules, opened, dissolved in water and given orally or via nasogastric tube, according to the feeding regime of each neonate (breast milk, donor milk or formula). Where concerns for NEC or LOS are present, probiotics will be stopped and reinstated once enteral feeds are recommenced.

Evaluation of effect of intervention

At 24 months corrected age there will be a Bayley-III scale test in an extensive examination performed by independent assessors, blinded to group allocation. After this evaluation, patients will be divided into four categories according to their degree of neurodevelopment: survival without neurodevelopment impairment (normal neurodevelopment), mild impairment, moderate impairment, or severe impairment²⁶. Mild impairment will be considered if they have muscle tone changes, impaired fine or gross motor coordination, Bayley scale score between 71-84, moderate behaviour disorders or mild visual

disability. Moderate impairment will be diagnosed when suffering from spastic diplegia, hemiplegia, seizures (non-febrile), Bayley scores between 50-70, severe behaviour disorders, moderate visual disability or mild-moderate hypoacusis. Severe impairment will be attributed to subjects with spastic quadriplegia, choreoathetosis, ataxia, Bayley score <50, blindness or severe hypoacusis.

Posteriorly, at 6 years of age, we will assess the presence of cerebral palsy, learning difficulties, behavioural disorders (autism spectrum, attention deficiency and hyperactivity disorder) and scores in the tests WISC-V, CBCL 6-18 and BRIEF-2. We will also perform a semi-structured interview to parents or legal guardians to determine the degree of impairment of the child, that might have not been previously included.

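### Section 5.1 requires survival to day 7 but not presence in the unit at day 7, so outborn infants first admitted later are eligible

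*Protocol*

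**What the plan says.** Protocol 5.1 admits infants under 32 weeks and under 1500 g "cared at BCNatal Hospital Clinic during years 2014-2019. Participants will have to survive beyond 7 days of life". The time condition in full is: "Participants will have to survive beyond 7 days of life (moment where the probiotic intervention will be given"). Section 6 gives the course as running "from 7 days of life until reaching a postmenstrual age of 34 weeks or discharge". Day 7 is thus the protocol's own time zero.

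Section 5 describes the unit as tertiary, and the variable list in 3.1 includes "Inborn vs Outborn", so infants transferred in are expected. The list has no item for age at admission. Section 5.2 excludes congenital, metabolic and genetic disease, suspected syndromes and unrelated later events. It says nothing about late admission.

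On the calendar, section 5 states: "There will be a 12 month wash out period (year 2017) to alleviate cross contamination of probiotics". Section 5.1 states: "Recruitment will start from January 2014 and will last until December 2019". Neither 5.1 nor 5.2 mentions 2017.

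**The concern.** The study is a non-randomised, sequential, single-centre comparison. It can be read causally only if infants in both groups enter at the same point and under the same conditions. Section 5.1 names that point but asks only that the infant be alive then, wherever it was.

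An infant first admitted on, say, day 20 differs from the intended cohort in three ways:

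- **Treatment.** The unit could not have started its course at day 7. Any exposure before arrival depended on another unit's practice.
- **Survival.** It had to live until transfer. Comparable infants who died elsewhere between day 7 and transfer never enter.
- **Outcome.** If it was transferred because of NEC or sepsis, it is in the cohort because of the event. Section 3 makes NEC, late-onset sepsis and mortality secondary outcomes.

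Counting events only from day 7 would not help, because the event can fall after day 7 and before arrival. Recording inborn or outborn status does not help either, since it does not separate a day-1 from a day-20 transfer. Section 7.2 names Mann-Whitney and chi-square tests with relative risks, and no adjustment. If referral patterns differ between the periods, a group difference can arise that has nothing to do with the product.

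**Working it through.** **1. Eligibility check by reading.** Take an outborn infant under 32 weeks and under 1500 g, without anomalies, first admitted on day 20.

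| Criterion | Met? |
|---|---|
| Gestation and weight (5.1) | yes |
| Cared for at the unit in 2014-2019 (5.1) | yes |
| Alive beyond day 7 (5.1) | yes |
| Any exclusion in 5.2 | none applies |
| Unit could start the course at day 7 (6) | no, but this is not a criterion |

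The infant is eligible as written.

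**2. Bias in NEC when the product has no effect (assumed inputs).** Let r be the NEC risk in infants present at day 7, s the share of late arrivals in a period, and q the proportion of late arrivals with NEC. The observed risk is (1 - s) × r + s × q. None of these three values is in the documents. I take r = 0.06 in both periods.

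| q | s = 2% | s = 4% | s = 6% |
|---|---|---|---|
| 0.30 | 0.98 × 0.06 + 0.02 × 0.30 = 0.0648 | 0.96 × 0.06 + 0.04 × 0.30 = 0.0696 | 0.94 × 0.06 + 0.06 × 0.30 = 0.0744 |
| 0.50 | 0.98 × 0.06 + 0.02 × 0.50 = 0.0688 | 0.96 × 0.06 + 0.04 × 0.50 = 0.0776 | 0.94 × 0.06 + 0.06 × 0.50 = 0.0864 |

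Relative risks between the periods:

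- Equal s and q in both periods: RR = 1.00, no bias.
- 2% v 4%: 0.0648/0.0696 = 0.93 and 0.0688/0.0776 = 0.89.
- 2% v 6%: 0.0648/0.0744 = 0.87 and 0.0688/0.0864 = 0.80. Reversed, these are 1.15 and 1.26.

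The direction depends on which period has more late arrivals, which the documents do not say.

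**3. Dilution of the neurodevelopmental contrast (assumed fraction).** The planned figure comes first. For 0.40 v 0.20, two-sided alpha 0.05 and power 80%, the usual formula gives (1.960 × √0.42 + 0.842 × √0.40)² / 0.20² = 81.2, so 82 per group. With continuity correction it gives 91. The stated minimum of 90 is consistent with the latter. Power at 90 per group, without the correction, is 83.9%.

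Now suppose that a fraction f of the probiotic group gets no benefit and keeps the control rate, so its rate is 0.20 × (1 - f) + 0.40 × f.

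| f | Rate | Power at 90 per group |
|---|---|---|
| 0 | 0.20 | 83.9% |
| 5% | 0.21 | 79.6% |
| 10% | 0.22 | 74.7% |

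This covers loss of contrast only, not selection on outcome. The true f is not in the documents.

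**4. The calendar, side by side.** Section 5 sets 2017 aside as a wash-out. Its subsection 5.1 gives one unbroken window of 72 months, of which 2017 is 12 (16.7%). Section 5 does not say in words that 2017 births are neither enrolled nor analysed, and 5.1 and 5.2 do not carry the wash-out over. No outcome arithmetic follows from this.

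**The case against.** **The intent is visible.** Section 5.1 links survival to the moment of intervention, which suggests a cohort available for treatment at day 7. That is fair, but it is an explanation in brackets and not a rule. Whoever applies the criteria to admission records could include a day-20 transfer without breaking any of them.

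**Nothing shows that late arrivals exist.** Outborn infants may all arrive on the first day. No passage reports an infant admitted after day 7, or one admitted with NEC. This stands, and it limits what can be said about size.

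**The relative risks rest on invented inputs and concern a secondary outcome.** This also stands. A threefold difference in late-arrival share has no basis in the documents, and equal shares and case mix give no bias. The lead objective is neurodevelopment, for which only the assumed dilution above can be shown.

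**A stronger reading on 2017.** A reader might infer from the unbroken window in 5.1 that 2017 births enter the comparison, and might then compute a loss of power from mixed exposure. The documents do not support this. Section 5 is the parent of 5.1, and the ordinary meaning of a wash-out year is that its births stay out. Reading 5.1 as overriding it would leave the wash-out without purpose. A power figure would also need assumptions about which period those births joined and what they received, and neither is documented.

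**Dates of birth or dates of care.** The date phrase in section 5 can be read as attaching to birth. That ambiguity is a reason to state birth dates plainly, for example for an infant born in December 2017 and still an inpatient in January 2018.

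**Conclusion.** The point holds for late arrivals. As written, 5.1 and 5.2 admit an infant first seen by the unit after the protocol's own time zero. Such an infant is selected on survival to transfer and possibly on the outcome, and the tests named in 7.2 do not correct for that. Eligibility is fixed in the protocol, so this is not a detail that can be left to a later analysis plan.

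The size is unknown. For NEC it ranges from none, with equal shares and case mix, to a relative risk of 0.87-0.80 (or 1.15-1.26 the other way) under the assumed 2% v 6%. These figures illustrate a mechanism and do not estimate its effect in this trial. For mortality the direction is open as well: sick transfers raise the risk, while selection on survival lowers it.

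The 2017 matter is a drafting inconsistency between section 5 and 5.1 that should be reconciled. It is not evidence that wash-out births are compared.

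**What to change.** - Reword 5.1 so that an infant must be alive and an inpatient of the unit at 7 days of life. Apply the rule identically to both periods.
- Report infants first admitted after day 7 separately, by period, so that their number and their condition on arrival can be seen.
- Define the two periods by birth date in 5.1 (January 2014 to December 2016, and January 2018 to December 2019), and state that 2017 births are outside the comparison, in line with section 5.

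The cost is a wording amendment and the extraction of birth and admission dates, which should be in the clinical record. A few late transfers would be lost, and the target population would narrow slightly to infants present at day 7. No clinical rule changes.

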5.2 Exclusion criteria

All neonates presenting with suspected congenital anomalies, inborn errors of metabolism, or genetic defects will be excluded. Infants with a suspected syndrome, or who had suffered events beyond the neonatal period, not related to prematurity, that could entail impairment in neurodevelopment (severe cranioencephalic trauma, oncological process, meningitis, or exposure to toxic substances) will also be excluded.

6 Treatment and study calendar

Intervention

Daily dose of 6x10⁹ UFC Infloran® -Berne, Switzerland- (Bifidobacterium bifidum NCDO 2203 and Lactobacillus acidophilus NCDO 1748) from 7 days of life until reaching a postmenstrual age of 34 weeks or discharge. The probiotic mixture will be provided in capsules, opened, dissolved in water and given orally or via nasogastric tube, according to the feeding regime of each neonate (breast milk, donor milk or formula). Where concerns for NEC or LOS are present, probiotics will be stopped and reinstated once enteral feeds are recommenced.

Evaluation of effect of intervention

At 24 months corrected age there will be a Bayley-III scale test in an extensive examination performed by independent assessors, blinded to group allocation. After this evaluation, patients will be divided into four categories according to their degree of neurodevelopment: survival without neurodevelopment impairment (normal neurodevelopment), mild impairment, moderate impairment, or severe impairment²⁶. Mild impairment will be considered if they have muscle tone changes, impaired fine or gross motor coordination, Bayley scale score between 71-84, moderate behaviour disorders or mild visual

disability. Moderate impairment will be diagnosed when suffering from spastic diplegia, hemiplegia, seizures (non-febrile), Bayley scores between 50-70, severe behaviour disorders, moderate visual disability or mild-moderate hypoacusis. Severe impairment will be attributed to subjects with spastic quadriplegia, choreoathetosis, ataxia, Bayley score <50, blindness or severe hypoacusis.

Posteriorly, at 6 years of age, we will assess the presence of cerebral palsy, learning difficulties, behavioural disorders (autism spectrum, attention deficiency and hyperactivity disorder) and scores in the tests WISC-V, CBCL 6-18 and BRIEF-2. We will also perform a semi-structured interview to parents or legal guardians to determine the degree of impairment of the child, that might have not been previously included.

On the other hand, at 6 years of age we will proceed to sampling of blood plasma for the study of different biomarkers related to neurodevelopment, inflammation, and intestinal permeability. We will analyse the following: NeuN, Doblecortina, GFAP, GDNF, Ki67, Nrf2, BDNF, NGF, neurotrophina-1 (NT-1), neurotrophina-3 (NT-3), neurotrophina-4 (NT-4), DYRK1A, HIF1 α , S100B i GSK3B. Regarding inflammation we will assess IL1B, IL6, IL8, IL10, IL12, TNF- α . We will finally determine presence of lipopolysaccharide in plasma with an ELISA.

7 Statistics

Considering an alpha risk of $\alpha = 0.05$ and a beta risk of $\beta = 0.2$ in a bilateral contrast, a minimum of 90 subjects in each group were required to detect a statistically significant difference between groups, where for the control group the proportion of some neurodevelopmental alteration was expected to be at least 0.4 and for the group treated with probiotics at least 0.2.

7.2 Statistical analysis

IBM SPSS Statistics 27.0.1.0 will be used for the statistical analysis. Non-parametrical analysis with a double-sided Mann-Whitney U test will be calculated for all continuous variables, whilst for categorical variables the chi-square test will be applied. In all cases, 0.05 will be considered the threshold of statistical significance. The relative risk (RR) and 95% confidence intervals will be determined for dichotomous variables. When encountering significant differences, the number needed to treat (NNT) will be analysed.

8 Ethics

The study will be in accordance with the Declaration of Helsinki (Fortaleza Version, Brazil October 2013) and will follow the legal requirements to fulfil the Spanish Biomedical Law of 14/2007. All patients, parents or legal guardians will be sought for informed consent.

9 Data processing and confidentiality

Treatment, communication and cease of data of personal character will be following the EU Ruling 2016/679 of the European Parliament and the Counsel of 27th April 2016, referring to protection of physical people and the treatment of personal data and the free circulation of data, being legally binding on the 25th of May 2018. The legal base of use of data will be in accordance to this act, established in the article 9 of EU 2016/679 Ruling.

All collected data will be deidentified and allocated a specific code, that will not allow any recognition of participants. Only the main promotor and collaborators will have access to data and will be allowed to enter the clinical history of patients for the purpose of this study.

Only legal requirement of medical emergency will allow the disclosure of any data related to participants of the study.

There will, however, be access upon request of non-identified data to Health Authorities, Ethics Committee and authorised personnel, for the purpose of quality assessment and study evaluation. Nevertheless, this will follow the existing legal frame and always guaranteeing confidentiality.

If data is to leave the EU, whether it is to entities related to the Hospital where patient was cared for, or third healthcare parties or collaborators, data will be protected via contracts or other established mechanisms to comply with EU legal requirements to data protection.

As the study promoters we agree to treat data in accordance to EU Ruling 2016/679, and therefore register all activities undertaken with the data and an assessment of data security and risks of the treatment of data.

Participants will be allowed to access, modify, oppose and cancel data (supress in the new ruling) and limit collected data as well as its processing. They will also be allowed to request copies or cession to a third party. In order to fulfil with their rights they will have to contact the Main promoter or the Delegate of Data Protection at Hospital Clinic I Provincial de Barcelona ([contact]). If they are not satisfied with the process they may contact the Data Protection Agency.

If a patient opts out of the study, their data will not be deleted to guarantee the validity of the research and fulfil their requirements with the healthcare authorities and pharmaceutical authorities.

The main promoter is obliged to preserve all collected data for the study for at least 5 years after the finalisation of the study. Posteriorly, personal information will only be stored by the Healthcare centre for healthcare purposes and the main researcher only if the patient has authorised such treatment, always in accordance to existing law.

10 Biological sampling and processing

We will proceed to collect 2 mL of blood plasma for the study of plasticity, inflammation and permeability biomarkers.

They will be analysed at the laboratory of Institut d'Investigacions Biomèdiques Agustí Pi i Sunyer (IDIBAPS) by [name] and [name].

After study completion all samples will be destroyed appropriately.

11 Funding

We will proceed to apply to national and international grants to achieve necessary funding (estimated 25,500€).

Researchers will receive no payments and all budget will be destined to pay for material and processing of samples, with some budget allocated to scientific sharing.

12 Publication policy

All results will be published in recognised peer review journals. Additionally, all participants will be entitled to dispose of their personal results for their convenience and discretion.

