
3 Objectives and purpose of the study

The objective of the study is to determine the effect of the combination of 2 probiotics (*Bifidobacterium bifidum* NCDO 2203 y *Lactobacillus acidophilus* NCDO 1748) in the neurodevelopment and neuroimage of extreme premature infants less than 32 weeks gestation and under 1500g at 2 years of age, and the neurodevelopment and neuronal plasticity biomarkers at 6 years of age.

Secondarily the incidence of necrotizing enterocolitis, late-onset sepsis, intraventricular haemorrhage and mortality of premature infants will also be assessed comparing those neonates that received probiotics from those that did not. Moreover, growth curves will be considered to determine the moment of "catch-up" (moment where the infant returns to his correspondent growth curves) between the two groups, and to elucidate whether there is any effect from the moment of "catch-up" and neurodevelopment. Finally, there will be a comparison between obesity, asthma, and respiratory disease at 6 years of age.

On the other hand, at 6 years of age there will be an assessment of neurodevelopment biomarkers and neuroplasticity in blood serum to determine changes in expression linked to probiotic administration, and therefore contribute to the enforcement of the existence of a brain-gut axis and its importance in neurodevelopment.

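### Non-randomised comparison of birth periods is analysed only with unadjusted two-group tests, although the prognostic factors needed for adjustment are collected

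*Protocol*

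**What the plan says.** Section 4 of the protocol calls the study a "Quasi-experimental, sequential, unicentric, cohort study". Section 5 takes births from January 2014 to December 2019 at one unit and adds: "There will be a 12 month wash out period (year 2017) to alleviate cross contamination of probiotics". No randomisation, matching or concurrent allocation is described. The years in which the probiotic was given are not stated; a comparison of birth periods is inferred from the sequential design and the wash-out year.

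Section 3 sets a causal aim: "The objective of the study is to determine the effect of the combination of 2 probiotics" on neurodevelopment at 2 and 6 years.

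Section 3.1 lists recorded variables without distinguishing outcomes from covariates. It includes "Gestational age, weight, length and head circumference at birth", sex, multiple gestation, IUGR, inborn or outborn status, antenatal steroids and "Cultural level of parents". None is given an adjusting role.

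Section 7.2 assigns tests by variable type: the "Mann-Whitney U test will be calculated for all continuous variables, whilst for categorical variables the chi-square test will be applied". It adds a relative risk with 95% confidence interval for dichotomous variables, and then: "When encountering significant differences, the number needed to treat (NNT) will be analysed". The protocol names no regression, stratification, weighting, matching or propensity method.

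**The concern.** In a randomised trial, crude two-group tests are defensible because allocation balances prognosis on average. Here allocation gives no such protection. Infants born in different years can differ in maturity, size, antenatal treatment or family background, and all of these can affect neurodevelopment. The named tests take no covariates. Applied to the baseline variables, they could show an imbalance but would not remove its effect on the outcome.

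At stake are the main neurodevelopmental comparison and any NNT drawn from it. An NNT reads as a statement about what treatment achieves; taken from a crude risk difference between non-randomised groups, it mixes case-mix with treatment. The direction of the bias is unknown, because the protocol does not say which years were treated and gives no baseline distributions.

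**Working it through.** **The plan's own figure.** Section 7 gives 90 per group for 0.40 against 0.20, two-sided alpha 0.05, power 80%. The usual two-proportion formula gives 82 per group, or 91 with continuity correction, so 90 is reproduced closely. It is a sample size for a crude comparison with no covariates.

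**Inputs from the protocol.** Control risk 0.40; 90 per group; two-sided 0.05.

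**Assumed inputs.** One binary prognostic factor with relative risk *k* for impairment, and prevalence *pc* in controls and *pp* in the probiotic group. The documents give none of these, so a range is shown.

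**Formula.** With no probiotic effect, the risk in the probiotic group is 0.40 × (1 + *pp*(*k* − 1)) / (1 + *pc*(*k* − 1)). For *k* = 2, 50% against 35%: 0.40 × 1.35 / 1.50 = 0.360, so the crude RR is 0.360 / 0.40 = 0.90. The rejection rate is the exact probability that the two-sided pooled two-proportion test (equivalent to chi-square) is significant.

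| *k* | Control vs probiotic prevalence | Probiotic-group risk | Crude RR | Significant results |
|---|---|---|---|---|
| any | balanced | 0.400 | 1.00 | 5.2% |
| 1.5 | 50% vs 40% | 0.384 | 0.96 | 5.8% |
| 2 | 50% vs 35% | 0.360 | 0.90 | 8.9% |
| 2 | 35% vs 50% | 0.444 | 1.11 | 9.2% |
| 3 | 50% vs 25% | 0.300 | 0.75 | 29% |
| 3 | 25% vs 50% | 0.533 | 1.33 | 42% |

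The last two rows are extremes. The risk without the factor is 0.40 / (1 + *pc*(*k* − 1)). For 50% vs 25% that is 0.40 / 2 = 0.20, against 0.60 with the factor. For 25% vs 50% it is 0.40 / 1.5 = 0.27, against 0.80.

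**Effect of adjusting.** In 200,000 simulated studies per scenario, Mantel-Haenszel stratification on the factor returned an RR of 1.00 with about 5% rejection in all four scenarios with *k* = 2 or 3.

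**A real effect can also be hidden.** With a true RR of 0.5, *k* = 2 and 35% vs 50%, the probiotic-group risk is 0.444 × 0.5 = 0.222. The crude RR is about 0.55 with power 74%; stratified, it is 0.50 with power 88%.

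**Precision.** For *k* = 2, 50% vs 35%, the SD of log RR was 0.195 crude and 0.190 stratified.

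**Calendar drift, a separate problem.** Assume the groups are 2014–16 and 2018–19. Their midpoints are 3.5 years apart. If the underlying risk falls by 3%, 5% or 8% a year from 0.40, then 0.40 × (1 − *r*)^3.5 gives 0.360, 0.334 or 0.299. The crude test is then significant in 9%, 15% or 30% of studies with no probiotic effect. The rates are the same whichever period was treated; only the direction changes. Covariate adjustment does not repair this, except where the drift runs through the covariates themselves.

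**The case against.** The strongest reply is that covariate lists and model forms are commonly left to a SAP, which is not at hand. Section 7.2 is short, does not call the RR crude and does not rule out adjustment. This does not carry the point. Section 7.2 is not silent: it assigns a test to every variable type, and those tests do not suit a causal question in a non-randomised design. The protocol has fixed an unsuitable method, which is different from leaving a detail open.

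Second, one centre, common eligibility (under 32 weeks and under 1500 g, alive beyond day 7), the exclusions and blinded 24-month assessment all limit bias. They do, but these limits still leave wide variation in maturity and size, and blinding protects measurement, not case-mix.

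Third, a large imbalance would usually be seen: at 90 per group, chi-square detects 50% vs 25% about 94% of the time and 50% vs 35% about 53%. Seeing an imbalance does not correct the RR, and the moderate one is missed nearly half the time.

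What stands is the caution about size. Every imbalance is assumed, the milder cases shift the RR by only 4% to 11%, small beside the planned RR of 0.5, and the top-end cases are extreme. It also stands that the data permit adjustment; what fails is the analysis as written. The drift figures are no argument for adjustment.

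**Conclusion.** The concern holds and should be fixed before analysis. Followed as written, section 7.2 mixes measured case-mix differences into the estimated probiotic effect and into any NNT.

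The actual bias cannot be computed from the protocol. On the assumed single-factor scenarios, the false-positive rate runs from 5.8% to 42% against 5.2% when balanced, with a crude RR between 0.75 and 1.33 where the truth is 1.00. The middle cases lie near 9%. The direction is not established. Adjustment resolves the measured part only; group and birth period remain aliased, provided the comparison is by period as the design implies.

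**What to change.** In section 7.2:

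- Make the main estimate a covariate-adjusted RR and risk difference for any impairment at 24 months, with adjusted mean differences for Bayley-III and WISC-V.
- Prespecify a short covariate set from section 3.1 that the intervention cannot affect: for example gestational age, birth weight or IUGR, sex, antenatal steroids and parental cultural level, the last only if recorded the same way in both groups.
- Do not adjust for variables arising after day 7, such as late-onset sepsis, necrotising enterocolitis or days of ventilation, which may lie on the path from treatment to outcome.
- Report crude results as secondary, and base any NNT on the adjusted risk difference.
- State which birth years form each group, that group and period are aliased, and that changes in care over time remain a limitation. Limit causal wording to match. Outcomes by birth year may be shown descriptively but cannot rule out drift.

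The cost is wording and a little more analysis, with no new data. Precision may fall modestly with several covariates; in the one-factor example it did not.

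### Age at growth catch-up falls under a Mann-Whitney rule that gives no place to children who have not caught up

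*Protocol*

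**What the plan says.** Section 3 of the protocol gives catch-up two uses. First, it is compared between groups: "growth curves will be considered to determine the moment of" catch-up, which is explained as the "moment where the infant returns to his correspondent growth curves) between the two groups". Second, it is an explanatory variable for neurodevelopment: the study is "to elucidate whether there is any effect from the moment of" catch-up on that outcome. Section 3.1 lists the moment of catch-up and the growth chart among the variables, with no unit, scale or measurement schedule.

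Section 7.2 divides all variables between two tests. For the first kind, a two-sided "Mann-Whitney U test will be calculated for all continuous variables"; for the second, "whilst for categorical variables the chi-square test will be applied". Relative risks with 95% intervals are added for dichotomous variables. No method for censored times is named, and nothing is said about a child who has not caught up. Section 5.1 requires survival only beyond day 7, so death before catch-up is possible.

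**The concern.** An age at catch-up exists only for a child who returns to the growth curve while being observed. Mann-Whitney needs a value, or at least a rank, for every child. Applied as written to recorded ages, it compares treated children who caught up with control children who caught up.

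That selects on something that happens after treatment and that treatment may change. If probiotics help more children catch up, the comparison gives no credit for it. If those extra children catch up late, their ages pull the treated group towards looking slower. The link with neurodevelopment has the same gap: children who never caught up, perhaps the most informative ones, have no value to enter.

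**Working it through.** **Inputs from the protocol.** Section 7: 90 per group, two-sided alpha 0.05, power 0.80, 0.4 v 0.2 for neurodevelopmental alteration. Section 4: comparison at 6 years, taken as 72 months.

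**The plan's own figure.** n = [1.96·√(2·0.3·0.7) + 0.8416·√(0.24 + 0.16)]² / 0.2² = (1.270 + 0.532)² / 0.04 ≈ 81.2, so 82 per group. With continuity correction: (81.2/4)·[1 + √(1 + 4/(81.2·0.2))]² ≈ 90.9, so 91. The stated 90 is therefore reproduced to within one. It does not concern catch-up and is used here only as the group size.

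**Assumptions.** The documents give no catch-up rate or timing. I took log-normal catch-up ages with median 18 months and log-SD 0.4 to 0.6. In the late scenarios the extra treated children catch up evenly between 36 and 71 months. There were 2000 simulated trials per setting (simulation error about 1 percentage point), with no deaths or losses.

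**Direct check of direction.** Let P be the chance that a treated child catches up earlier than a control child, with 0.5 meaning no difference.
- 60% v 80%, equal timing, caught-up children only: P = 0.5. The benefit cannot be seen.
- 60% v 80%, extra 20 points late, caught-up children only: 60/80 = 0.75 of treated children who caught up share the control timing and 0.25 are later, so P ≈ 0.75·0.5 + 0.25·0 = 0.375. This points against treatment.
- The same late case with children who never caught up ranked last: P = 0.6·(0.6·0.5 + 0.4) + 0.2·0.4 + 0.2·0.4·0.5 = 0.42 + 0.08 + 0.04 = 0.54. This points towards treatment.

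**Simulated results** (share of trials significant; range over log-SD 0.4 to 0.6):

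| Control v treated | Mann-Whitney, observed ages: for / against treatment | Mann-Whitney, not caught up ranked last: for | Log-rank: for |
|---|---|---|---|
| 60% v 80%, equal timing | 2–3% / 2–3% | 65–67% | 79–81% |
| 70% v 85%, equal timing | 2–3% / 2–3% | 40–41% | 56–59% |
| 60% v 80%, extra late | 0% / 62–66% | 16–18% | 47–49% |
| 60% v 70%, extra late | 0% / 24–26% | 8% | 14–15% |
| 85% v 90%, extra late | under 1% / 7–8% | 2–4% | 5–6% |

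Other runs of the 20-point late case, including one with normally distributed ages (means 18 and 48 months, SD 6), gave 67% to 68% against treatment. About 2.5% in each direction is chance.

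**Proportional hazards.** With exponential times and a hazard ratio of 1.5, the direction is kept on average and the loss is of power. With a control median of 24 months, P = 0.57, and Mann-Whitney on observed ages is significant in 37% of trials against 74% for log-rank. With a control median of 48 months, P = 0.54 and the figures are 12% against 64%.

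**The case against.** - **Exclusion is not written.** A reader might infer that the protocol tells the analyst to drop children who have not caught up. It does not; that is the default result of ranking recorded ages. Ranking those children last would also satisfy section 7.2, and the table shows that it removes the reversal and most of the power loss when timing is equal. This objection stands. However, no such rule is stated, it recovers less when the extra catch-up is late (16–18% against 47–49%), and it does not deal with death or loss before catch-up.
- **The scale is not stated.** Catch-up recorded by visit or age band could be treated as categorical, with a category for not caught up, and chi-square would apply. The concern depends on catch-up being recorded as an age, which is the natural reading of a moment but an assumption.
- **Reversal is a special case.** A reader might infer that the comparison will come out backwards. That needs extra catch-up concentrated late, and it shrinks quickly with the number of extra children. At 5 extra points it is close to chance, and log-rank has little power there too.
- **Unequal follow-up is not shown.** The protocol sets a common 6-year comparison. Deaths and losses can occur, but it gives no amounts.
- **It could be left to an analysis plan.** Handling of missing values often is. Here, though, the protocol fixes the test for every continuous variable, so an analysis plan would have to depart from it to treat this outcome properly.

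**Conclusion.** The point holds in a limited form. If catch-up is recorded as an age, the test fixed in section 7.2 does not suit the comparison that section 3 announces, because it has no place for children who have not caught up. The harm shown most consistently is lost information: about 5% significance (chance level) against about 80% for log-rank at 60% v 80% with equal timing, and roughly half or less of the log-rank power under the proportional-hazards cases. Significance in the wrong direction is conditional on late extra catch-up: 62% to 68% of trials with 20 extra points, about 26% with 10 and about 8% with 5. All these figures rest on assumed rates and timing.

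A reader might infer that the main result is at risk. It is not: catch-up is introduced as secondary, and the sample size and main neurodevelopment comparison do not depend on it. The change should be made, but it is not critical.

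**What to change.** In section 7.2, exempt catch-up time from the Mann-Whitney rule and state:

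- **Who is at risk:** children below their growth curve at a stated starting point. A child who never left the curve has no catch-up to time.
- **What is measured:** which growth measure and which threshold define return to the curve.
- **Clock:** one only, for example corrected age.
- **Analysis:** time to catch-up, censored at the last growth measurement, with death as a competing event; Kaplan-Meier or cumulative incidence curves and a log-rank or Cox comparison.
- **Fixed ages:** the proportion caught up at 2 and at 6 years by group, with 95% CI.
- **Link with neurodevelopment:** caught-up status at a fixed age no later than the assessment concerned, so that children who have not caught up stay in the analysis.

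The cost is a short paragraph and slightly more analysis work, using the growth charts already listed in section 3.1. One limit remains: catch-up is known only to the nearest measurement, so the times are approximate, and this should be acknowledged when they are reported.
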